2.2. Final Analysis

The [REDACTED] will perform the production and quality control of all tables, figures and listings on behalf of Urovant Sciences, Inc.

Statistical programming will start after data have been collected and are available in the database. Blinded dry-runs using dummy treatment code will be performed prior to database lock and unblinding to ensure programming displays and algorithms are developed as planned. The planned final end-of-study analysis will be performed once the final clinical database lock (after all subjects complete the study or exit the study prematurely) has been achieved and treatment codes have been unblinded to the statistics and programming team. The clinical study report will be based on final analysis results.

2.3. Data and Safety Monitoring Board

A DSMB will be retained to assess, on an ongoing basis, all safety aspects of this study including unblinded review of safety data after all subjects reach Week 6 (or prematurely discontinue) in Cohort 1 (URO-902 24 mg). Randomization at the higher dose (URO-902 48 mg) will begin only after the DSMB has recommended it is safe to proceed to Cohort 2. This committee will be an external independent DSMB that monitors safety. The detailed activities including meeting plans will be described and documented in the DSMB Charter. A separate statistical analysis plan may be prepared for the DSMB.

3. ANALYSIS POPULATION

3.1. Analysis Population

3.1.1. Screened Population

The screened population consists of all subjects who are screened for the study. This population is used primarily for subject accounting purposes and will generally not be used for summary or analysis.

3.1.2. Randomized Population

The randomized population consists of all subjects who are randomized to receive any double-blind study drug regardless of whether they received the study drug.

3.1.3. Safety Population

The safety population consists of all subjects from Cohorts 1 and 2 who were randomized and received study drug and will be used to analyze all safety endpoints based on actual treatment received.

3.1.4. Intent-to-treat Exposed (ITT-E)

The ITT-E population consists of all subjects who are randomized and treated from Cohorts 1 and 2. ITT-E will be used for demographics, baseline characteristics, and efficacy analyses. Subjects will be included in the treatment group to which they are randomized.

3.2. Violations and Deviation

Subjects who do not meet eligibility criteria but are still randomized will be analyzed according to the analysis population described in [Section 3.1](#).

3.2.1. Protocol Deviations

The final list of major protocol deviations will be finalized and documented prior to database lock except for the deviation category of wrong treatment which will be confirmed upon study unblinding. Only major protocol deviations will be summarized and listed in the Clinical Study Report (CSR). Major deviations will be those which are considered to potentially impact upon the interpretation of the primary efficacy endpoint in the study or may potentially impact the interpretation of safety. Major protocol deviation categories may include, but are not limited to the following:

- Randomized subjects who do not meet the inclusion criteria
- Randomized subjects who meet any of the exclusion criteria
- Subjects who received the wrong treatment

- Concomitant use of prohibited medications not approved by the medical monitor
- Randomized subjects who met withdrawal criteria during the study but were not withdrawn

Due to the limited sample size of the study, no sensitivity analysis will be performed on a per-protocol population.

4. GENERAL STATISTICAL CONSIDERATIONS

4.1. General Principles for Data Analysis

The general formats and layouts of tables, listings, and figures (TLFs) are provided in a separate “programming consideration” document. Actual formats and layouts may be altered slightly to accommodate actual data or statistics. Minor format changes will not require updates to the SAP.

The TLF numbering and general content follow the ICH E3 guidelines.

4.1.1. Multicenter Study

In this study the stratified permuted block randomization is not done within centers. The analyses will be conducted by pooling data from all study centers and will not include study center as a covariate in the statistical modeling.

4.1.2. Testing Strategy and Multiplicity Adjustments

No formal multiplicity adjustment will be performed. Nominal p-values will be provided for all exploratory efficacy analysis as a measure of the strength of association between the endpoint and the treatment effect rather than formal tests of hypotheses.

4.1.3. Examination of Subgroups

To determine whether the treatment effect is consistent across various subgroups, the efficacy endpoints related to UUI, micturitions, UI, and urgency episodes will be summarized descriptively for each of the following subgroups:

- Baseline UUI episodes per day (≤ 3 vs >3)
- Presence or absence of DO
- Previous use of onabotulinumtoxinA (naïve vs. prior use)

Baseline UUI episodes per day will be based on the actual value collected at baseline, presence or absence of DO will be based on the central reader’s assessment on the urodynamics form, and prior onabotulinumtoxinA use will be based on the randomization stratification from the new randomization scheme after the amendment 1. The subjects enrolled in Cohort 1a will be considered onabotulinumtoxinA naïve.

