## 9.7. Subgroup Analyses

Subgroup analyses of endpoints may be conducted. Additional details of any planned subgroup analyses will be provided in the SAP.

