4.2.2. Reporting Conventions

General rules

In general, all collected safety data, any derived efficacy parameters from the bladder diary, questionnaire data, and urodynamic data will be presented in subject data listings. Listings will be ordered by treatment, subject number, and assessment week or event date. The treatment group presented in listings will be based on the planned assignment for efficacy endpoints and actual assignment for safety endpoints.

Summary tables will be provided for all randomized subjects. All demographic and baseline data will be presented by treatment arm and overall, unless otherwise specified. Bladder diary, questionnaire, urodynamic data, and safety data will be presented by treatment arm only. In general, continuous variables will be summarized to include the population sample size (N), number of subjects with available data (n), arithmetic mean, standard deviation (SD), median, minimum, Q1, Q3 and maximum values. Categorical variables will be summarized by the population size (N), number of subjects with available data (n), number of subjects in each category, and the percentage of subjects in each category. Unless otherwise noted, the denominator to determine the percentage of subjects in each category will be based on the number of subjects with available data (n) in the analysis set of interest. Selective ordinal data may be summarized using both descriptive statistics as well as counts and percentages of subjects in each category, as appropriate.

The data analyses will be conducted using the SAS® System (SAS Institute Inc., Cary, NC) version 9.3 or above. The eClinical Solutions' standard operating procedures will be followed for the validation of all SAS programs and outputs.

Formats

Numeric data will be reported at the precision collected on the electronic case report form (eCRF). The reported precision from non eCRF sources may be adjusted to a clinically interpretable number or decimal places.

Unscheduled Visits

Unscheduled visits will be assigned to an analysis visit using the all-inclusive windows defined in [Section 4.2.4](#). If multiple assessments are done in the same visit, the selection rule in [Section 4.2.4](#) will apply. All assessments at unscheduled visits will be included for deriving last post-baseline or maximum value post-baseline and in the data listings.

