6.1. Continuous Efficacy Endpoints

For continuous efficacy endpoints, the by-visit means and SD, as well as change from baseline estimated with least squares means, standard error, and 95% confidence intervals (CI) will be presented for each treatment group and the difference between each dose group relative to placebo. Nominal p-values from comparisons from each dose group relative to placebo will be provided for descriptive purposes. The change from baseline will be analyzed by a mixed model for repeated measures (MMRM) with restricted maximum likelihood estimation incorporating all applicable post-baseline visits. For average daily number of urge urinary incontinence (UII) episodes, the MMRM model will include terms for treatment, visit, visit by treatment interaction term, baseline value, and previous use of onabotulinumtoxinA as randomized (naïve vs. prior use). For the other endpoints, one additional term of baseline UII episodes per day category as randomized (≤ 3 vs. > 3) will be included in the MMRM model. If any of the stratification factors has a stratum with number of subjects less than 5, the factor in question will not be included in the MMRM model. If $>15\%$ of the subjects were incorrectly stratified based on the actual baseline UII episodes per day and previous use of onabotulinumtoxinA, a sensitivity analysis using the same MMRM model but with actual values of the two stratification factors as covariates will be carried out.

The Kenward-Roger adjustment will be used with restricted (or residual) maximum likelihood (REML) to make statistical inference. An unstructured covariance matrix will be used to model the correlation among repeated measurements. If the unstructured covariance model fails to converge with the default Newton-Raphson algorithm, the Fisher scoring algorithm will be used to provide initial values of the covariance parameters. In the rare event that none of the above methods yield convergence, the following structures will be investigated: heterogeneous Toeplitz, Toeplitz, heterogeneous First-Order Autoregressive [AR (1)],

heterogeneous compound symmetry (HCS), and compound symmetry (CS). The covariance structure converging to the best fit, as determined by Akaike's information criterion (AIC), will be used.

[figure not shown]

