11. APPENDIX

11.1. Table of Contents for Data Display Specifications

11.1.1. Output Tables

Table 8: List of Output Tables

Title		Population	Programming Note	Deliverable
Study Population				
14.1.1.1	Subject Enrollment	Scanned		EOS
14.1.1.2	Subject Disposition	Randomized		TL, EOS
14.1.1.3	Subject Randomization by Investigator	Randomized		EOS
14.1.2.1	Major Protocol Deviations	Randomized		EOS
14.1.2.2	Reasons for Exclusion from Analysis	Randomized		EOS
14.1.3.1	Demographics and Baseline Characteristics	ITT-E		TL, EOS
14.1.4	Medical History	ITT-E		EOS
14.1.5.1	Prior Medication	ITT-E	ATC Level 2 and 4	EOS
14.1.5.2	Concomitant Medication	ITT-E	ATC Level 2 and 4	EOS
14.1.5.3	Additional OAB Treatment Received Prior to Week 24 (Medication)	ITT-E	ATC Levels 2, 4 and PT	TL, EOS
14.1.5.4	Additional OAB Treatment Received at or After Week 24 (Medication)	ITT-E	ATC Levels 2, 4 and PT	TL, EOS
14.1.5.5	Additional OAB Treatment Received Prior to Week 24 (Procedure)	ITT-E	ATC Levels 2, 4 and PT	EOS

Title		Population	Programming Note	Deliverable
14.1.5.6	Additional OAB Treatment Received at or After Week 24 (Procedure)	ITT-E	ATC Levels 2, 4 and PT	EOS
14.1.6	COVID-19 Impact	ITT-E		EOS
Efficacy Endpoints				EOS
14.2.1.1	Change from Baseline in Average Daily Number of Urge Urinary Incontinence Episodes (MMRM)	ITT-E	Week 12 first, then other visits sequentially	TL, EOS
14.2.1.2	Summary of Average Daily Number of Urge Urinary Incontinence Episodes	ITT-E	By-visit Descriptive Summary	TL, EOS
14.2.1.3	Summary of Average Daily Number of Urge Urinary Incontinence Episodes by Baseline UUI Episodes per Day	ITT-E	Subgroup columns within each treatment arm	EOS
14.2.1.4	Summary of Average Daily Number of Urge Urinary Incontinence Episodes by Presence or absence of DO	ITT-E	Subgroup columns within each treatment arm	EOS
14.2.1.5	Summary of Average Daily Number of Urge Urinary Incontinence Episodes by Previous Use of onabotulinumtoxinA	ITT-E	Subgroup columns within each treatment arm	EOS
14.2.1.6	Change from Baseline in Average Daily Number of Urge Urinary Incontinence Episodes at Week 12	ITT-E		EOS
14.2.1.7	Change from Baseline in Average Daily Number of Urge Urinary Incontinence Episodes (MMRM) - Sensitivity Analysis	ITT-ES	Week 12 first, then other visits sequentially	EOS
14.2.2.1	Change from Baseline in Average Daily Number of Micturitions (MMRM)	ITT-E	Week 12 first, then other visits sequentially	TL, EOS

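### SAP 4.1.3 aims to determine whether the treatment effect is consistent across subgroups but plans only by-arm summaries, with no subgroup difference from placebo, interval or between-level contrast

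*SAP*

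**What the plan says.** Protocol 9.7 leaves the method to the SAP: "Additional details of any planned subgroup analyses will be provided in the SAP".

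SAP 4.1.3 opens with the aim "To determine whether the treatment effect is consistent across various subgroups" and then gives the method: "the efficacy endpoints related to UUI, micturitions, UI, and urgency episodes will be summarized descriptively for each of the following subgroups". The three factors are baseline UUI (3 or fewer vs more than 3 per day), presence or absence of DO by central reading, and prior onabotulinumtoxinA use.

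SAP 4.2.2 defines what a continuous summary contains: N, n, then "arithmetic mean, standard deviation (SD), median, minimum, Q1, Q3 and maximum values". It adds that "Bladder diary, questionnaire, urodynamic data, and safety data will be presented by treatment arm only".

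The output list in SAP 11.1.1 has twelve subgroup tables: 14.2.1.3 to 14.2.1.5, and the matching sets under 14.2.2, 14.2.3 and 14.2.4. All are titled as summaries and carry the layout note "Subgroup columns within each treatment arm".

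Least squares mean differences from placebo with 95% intervals are specified in SAP 6.1 for the whole ITT-E population. For UUI, "the MMRM model will include terms for treatment, visit, visit by treatment interaction term, baseline value, and previous use of onabotulinumtoxinA as randomized"; the other endpoints add the baseline UUI category. No treatment-by-subgroup term appears, and the figure list in SAP 11.1.2 has no subgroup figure.

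**The concern.** The aim concerns a treatment effect, which here means a difference from placebo, and whether that difference changes between levels of a factor. The method yields neither quantity. A team that follows the SAP exactly will have arm means by level, and anyone wanting an answer must subtract them by eye.

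Two features make that unsafe. First, the cells are small: about 11 or 12 subjects per arm at an even split, and about 6 and 17 at 25:75. Second, the means are not adjusted for baseline. This matters most for DO. It was a randomization factor only in Cohort 1a, by the investigator's reading (Protocol 6.5), whereas the subgroup uses the central reader's. The arms are therefore not balanced within DO levels by design.

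What is at stake is interpretation of the subgroup tables in the study report: a chance pattern may be taken as a difference in effect, or a real difference passed over.

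**Working it through.** **Inputs.** From SAP 1.2.4: 23 evaluable per dose group and 23 in pooled placebo, SD 2.86, difference 1.8 UUI episodes/day, two-sided alpha 0.05. The documents give no subgroup shares; Protocol 6.5 only caps prior onabotulinumtoxinA use at 50% per cohort. Shares from 50:50 to 20:80 are therefore assumed, equal across arms, with SD 2.86 in every level and no gain from baseline adjustment.

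**The plan's own figures.** Two-sample t-test power (noncentral t, 44 df) is 55.1%, against the stated 55%. The half-width is t(0.975, 44) × 2.86 × √(2/23) = 2.015 × 0.843 = 1.70, as stated.

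**Precision in subgroups.** With *m* subjects per arm in a level, half-width = t(0.975, 2m − 2) × 2.86 × √(2/m). With *a* and *b* per arm in the two levels (a + b = 23), the SE of the difference between the two effects is 2.86 × √(2/a + 2/b), with 42 df and t = 2.018.

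At 12/11:
- Within levels: 2.074 × 2.86 × √(2/12) = 2.42, and 2.086 × 2.86 × √(2/11) = 2.54.
- Between levels: SE = 2.86 × √(2/12 + 2/11) = 1.69; half-width = 2.018 × 1.69 = 3.41.

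| Split (per arm) | Half-widths within levels | Half-width between levels | Chance that one gap is ≥ 1.8 with no true difference |
|---|---|---|---|
| 50:50 (12/11) | 2.42, 2.54 | 3.41 | 29% |
| 30:70 (7/16) | 3.33, 2.07 | 3.70 | 33% |
| 25:75 (6/17) | 3.68, 2.00 | 3.88 | 35% |
| 20:80 (5/18) | 4.17, 1.94 | 4.13 | 38% |

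The last column is 2 × [1 − Φ(1.8/SE)]. At 12/11, 1.8/1.69 = 1.07, giving 29%.

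**Across all the looks for one endpoint.** Three factors and two doses give 3 × 2 = 6 between-level gaps and 3 × 2 × 2 = 12 subgroup effects. In 20,000 simulated trials per scenario, the true effect was 1.8 in every subgroup, the factors were independent and membership was random. The shares were all 50%; then 50%, 60% and 70%; then 40%, 30% and 25%.
- At least one of six gaps of 1.8 or more: 85%, 87% and 90%. With splits fixed at exactly 12/11 it is about 83%.
- At least one of twelve effects zero or reversed: 40%, about 44% and 50%. For a single effect it is about 7% to 8%.

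**Power.** The chance of detecting a true between-level difference of 1.8 at two-sided 0.05 is about 18% at 50:50 and 14% at 20:80.

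**The case against.** The strongest defence is that the study is exploratory, has no formal hypothesis (Protocol 9.1) and treats all efficacy endpoints as descriptive (Protocol 9.6). At this size, descriptive subgroup tables are a defensible choice. That stands as a limit on the weight of the point. It does not remove the mismatch, because SAP 6.1 already gives intervals for equally exploratory endpoints, and estimates with intervals need no hypothesis.

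A reader might infer that the tables carry no measure of error. They do: SAP 4.2.2 provides n and SD, so an unadjusted difference and interval can be worked out by hand. What is missing is the baseline-adjusted effect and any printed interval or contrast.

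A reader might take 85% to 90% as the risk for each comparison, or as proof that the tables will look inconsistent to their readers. It is the chance of at least one gap among six, on assumed shares; for one comparison it is roughly a third.

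A reader might also infer that these subgroups will select the next trial's population. Neither document says so.

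It is fair, too, that intervals will not settle consistency: power for a between-level difference of 1.8 is only 14% to 18%. The baseline UUI factor has a further problem. A subject at 3 or fewer episodes/day cannot fall by more than 3, and one at the entry minimum of 1 (Protocol 5.1) cannot fall by 1.8. A contrast in absolute change may reflect that floor alone, and a common SD and effect are doubtful there.

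Other text does not fill the gap. SAP 4.1.2 promises nominal p-values for exploratory efficacy analyses, but SAP 4.1.3 and the table list confine subgroups to summaries. The allowance in SAP 9 for data-driven sensitivity analyses is not a subgroup plan. Table layouts sit in a separate document not available here, but the SAP's titles and notes point to summaries only.

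**Conclusion.** The point holds as a mismatch between aim and method. Following SAP 4.1.3 as written produces no subgroup treatment effect, no interval and no between-level comparison, so it cannot show whether the effect is consistent. Under the SAP's SD and sample size, the unprinted uncertainty is large: about 2.4 to 2.5 episodes/day within a level and 3.4 between levels at an even split, rising to 3.7 to 4.1 between levels at 30:70 to 20:80. That is roughly twice the assumed effect or more.

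These sizes rest on assumed shares, a common SD in every level and no gain from baseline adjustment, which would narrow the intervals. The consequence is confined to how subgroup results are reported and read. The documents do not support extending it to the overall dose comparisons, which do not depend on these tables.

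**What to change.** In SAP 4.1.3:

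1. Keep the twelve descriptive tables.
2. For Week 12 change in UUI episodes and micturitions, extend the ANCOVA already planned in SAP 6.1 (treatment and baseline value) with subgroup and treatment-by-subgroup terms, one factor at a time. For each dose, report the baseline-adjusted difference from pooled placebo with its 95% CI in each level, and the between-level difference in that effect with its 95% CI. No tests are needed.
3. Give descriptive results only where an arm-by-level cell is very small, for example fewer than 5 subjects. This would be a new rule: the threshold of 5 in SAP 6.1 decides whether a stratification factor enters the MMRM and does not apply to arm-by-level cells.
4. Change *To determine* to *To explore*, and state that the intervals are too wide to establish consistency.
5. Note that for baseline UUI an absolute-change contrast may reflect the floor on possible reduction, so the between-level interval alone should not decide consistency for that factor.

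The ANCOVA is preferable to adding a three-way term to the MMRM. With seven post-baseline diary visits, that model would need 3 × 2 × 7 = 42 cell means and 7 × 8/2 = 28 covariance parameters from about 3 × 23 = 69 evaluable subjects.

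The cost is SAP wording and a few extra model runs on data already collected. The drawback is that the intervals will be visibly wide.

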4.2. General Data Handling Conventions

4.2.1. Study Treatment Description

Randomized treatment groups will be displayed as shown in the following table:

Data Displays for Reporting	
Description	Order in TLF
Placebo	1
URO-902 24 mg	2
URO-902 48 mg	3
Overall (if applicable)	4

For the reporting done within each cohort, the treatment group applicable to the cohort will be used in the output (i.e. URO-902 24 mg for Cohort 1 and URO-902 48 mg for Cohort 2).

4.2.2. Reporting Conventions

General rules

In general, all collected safety data, any derived efficacy parameters from the bladder diary, questionnaire data, and urodynamic data will be presented in subject data listings. Listings will be ordered by treatment, subject number, and assessment week or event date. The treatment group presented in listings will be based on the planned assignment for efficacy endpoints and actual assignment for safety endpoints.

Summary tables will be provided for all randomized subjects. All demographic and baseline data will be presented by treatment arm and overall, unless otherwise specified. Bladder diary, questionnaire, urodynamic data, and safety data will be presented by treatment arm only. In general, continuous variables will be summarized to include the population sample size (N), number of subjects with available data (n), arithmetic mean, standard deviation (SD), median, minimum, Q1, Q3 and maximum values. Categorical variables will be summarized by the population size (N), number of subjects with available data (n), number of subjects in each category, and the percentage of subjects in each category. Unless otherwise noted, the denominator to determine the percentage of subjects in each category will be based on the number of subjects with available data (n) in the analysis set of interest. Selective ordinal data may be summarized using both descriptive statistics as well as counts and percentages of subjects in each category, as appropriate.

The data analyses will be conducted using the SAS® System (SAS Institute Inc., Cary, NC) version 9.3 or above. The eClinical Solutions' standard operating procedures will be followed for the validation of all SAS programs and outputs.

Formats

Numeric data will be reported at the precision collected on the electronic case report form (eCRF). The reported precision from non eCRF sources may be adjusted to a clinically interpretable number or decimal places.

Unscheduled Visits

Unscheduled visits will be assigned to an analysis visit using the all-inclusive windows defined in [Section 4.2.4](#). If multiple assessments are done in the same visit, the selection rule in [Section 4.2.4](#) will apply. All assessments at unscheduled visits will be included for deriving last post-baseline or maximum value post-baseline and in the data listings.

